#### 4.1.1 Dose Escalation Phase

The goal of the Dose Escalation Phase of this study is to initially characterize the safety and tolerability of MGC018 administered alone or in combination with MGA012 and, more specifically, to define the MTD of these respective monotherapy and combination regimens. If no MTD is defined during the dose escalation of MGC018 monotherapy (Module A) after escalation to the maximum protocol-specified dose, then that dose level will be designated as the MAD for MGC018 monotherapy. Similarly, if no MTD is defined during dose escalation of the combination of MGC018 and MGA012 (Module B), after escalation to the maximum protocol-specified dose, then that dose level will be designated as the MAD for MGC018 and MGA012 combination therapy.

For the purposes of guiding decisions regarding dose escalation, the **DLT Evaluation Period** for Module A (monotherapy) will be 21 days following administration of the first dose of MGC018. For Module B (combination therapy), the DLT evaluation period will be 42 days in duration.

Dose escalation will follow a conventional 3+3+3 design: successive cohorts of 3 to 9 participants each will be evaluated in sequential escalating doses of MGC018 administered alone (Module A) or in combination with MGA012 (Module B) as shown below (**Table 3** and **Table 4**).

Sentinel dosing will be used for the first 2 dose levels. The first administration of MGC018 in participants in the first 2 dose levels in Module A will be staggered by at least 48 hours.

In Module B, MGA012 will be administered at a dose of 375 mg (flat dose) Q3W, beginning on Day 22 of Cycle 1, and continuing on Days 1 and 22 of every cycle thereafter.

Participants who require dose delays greater than 21 days secondary to AEs considered unrelated to study treatment or any other cause unrelated to study treatment are considered unevaluable for safety and toxicity during the DLT evaluation period and will be replaced.

Intermediate dose levels may be explored based on review of the cumulative safety data and upon agreement between the investigators and the sponsor.

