## 4.2 Dose Limiting Toxicity

For the purposes of guiding study decisions regarding dose escalation, DLTs will be based on study drug-related AEs or laboratory abnormalities that occur up to Study Day 21 of Cycle 1 in the Dose Escalation Phase only for Module A and Study Day 42 of Cycle 1 in the Dose Escalation Phase only for Module B. The severity of AEs will be graded according to the National Cancer Institute Common Terminology Criteria for Adverse Events version 4.03 (NCI CTCAE v4.03). Dose-limiting toxicities will be defined separately for hematologic, non-hematologic, and hepatic non-hematologic events.

In general, for participants who experience toxicity that may meet the criteria for a DLT, subsequent administration of the study drugs should be held pending management and/or resolution of the event and assessment of attribution to the study drug. Criteria for discontinuation of therapy are outlined in [Section 5.4](#).

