#### **4.3 Dose Escalation Rules**

The Dose Escalation Phase of this trial will proceed using a conventional 3 + 3 + 3 approach.

If 0 of the first 3 participants treated at a given dose level experience a drug-related DLT during the DLT evaluation period, the dose will be escalated, and 3 participants will be enrolled and treated at the next higher dose level (up to the planned highest dose level).

If 1 of the first 3 participants treated at a given dose level experiences a drug-related DLT, then 3 additional participants will be enrolled at that dose level (thus making a total of 6 participants in this cohort) to further assess the safety of MGC018 alone (Module A) or in combination with MGA012 (Module B).

- If  $\geq 2$  of these 3 additional participants (i.e.,  $\geq 3$  of the 6 participants enrolled in the cohort) experience a DLT, it will be concluded that the MTD has been exceeded, and 3 participants will be enrolled and treated at the next lower dose level.
- If 1 of these 3 additional participants experiences a drug-related DLT, then another 3 additional participants (for a total of 9 participants in the cohort,  $3 + 3 + 3$ ) will be enrolled and treated at that dose level to further characterize the safety of MGC018 alone (Module A) or in combination with MGA012 (Module B).
- If 0 of the 3 additional participants experiences a DLT, then the dose will be escalated, and 3 participants will be enrolled at the next higher dose level.

If  $\geq 2$  participants out of the first 3 participants treated at a given dose level, or  $\geq 3$  of 6 participants treated at a given dose level, or  $\geq 3$  out of 9 participants treated at a given dose level experience a drug-related DLT, then it will be concluded that the MTD for MGC018 alone (Module A) or in combination with MGA012 (Module B) has been exceeded at that dose level, and all subsequent participants will be treated at the next lower dose level.

If  $\geq 2$  participants out of the first 6 participants treated at a given dose level experience the same drug-related DLT, then the enrollment in that cohort will stop, and it will be concluded that the MTD for MGC018 alone (Module A) or in combination with MGA012 (Module B) has been exceeded and all subsequent participants will be treated at the next lower dose level. In categorizing DLTs, all related MedDRA Preferred Terms will be used to determine whether the same DLT has occurred in a given cohort.

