If  $\geq 2$  participants out of the first 6 participants treated at a given dose level experience a Grade 4 DLT, then the enrollment in that cohort will stop, and it will be concluded that the MTD for MGC018 alone (Module A) or in combination with MGA012 (Module B) has been exceeded and all subsequent participants will be treated at the next lower dose level.

For participants being treated at a dose level subsequently determined to exceed the MTD for a given cohort of the study, the dose of MGC018 alone (Module A) or in combination with MGA012 (Module B) will be reduced to the next lower dose level as summarized in [Table 3](#) and [Table 4](#). Following these rules for dose escalation, the MTD/MAD will be the highest dose administered during the Dose Escalation Phase of the study at which the incidence of DLT is  $< 33\%$ .

Dose escalation to the next dose level is permitted only after the participants enrolled in the current dose cohort have completed the DLT evaluation period and the safety data have been reviewed by the sponsor medical monitor, Independent Safety Monitor, and the investigators participating in the study. Evaluation of safety data from each cohort will include an assessment of the proportion of participants who receive planned doses, and the percentage of participants that require dose reductions or dose discontinuations for toxicity. The sponsor medical monitor, Independent Safety Monitor and investigators will consider all available data from participants both during and beyond the DLT evaluation period when making dose escalation decisions and in the determination of the recommended phase 2 dose to be evaluated in expansion cohorts. In particular, if a Grade 4 febrile neutropenia has been observed, the sponsor will review and evaluate the safety database for other events of any grade febrile neutropenia prior to making a decision to dose escalate.

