#### 4.4.2 Dose Delays

Participants who experience toxicity should have study drug held pending assessment, management, and resolution of the toxicity. Participants in whom the toxicity is assessed to be unrelated to study drug or for whom the toxicity does not meet the criteria for discontinuation, may reinstitute study drug as per guidelines outlined in [Section 4.4.1](#) and [Section 7](#). Reinstitution of study drug shall be conducted as follows:

- For participants in whom the toxicity is assessed to be related to study drug, dose delays of up to 21 days are allowed.
- For participants in whom the toxicity is unrelated to study drug, dose delays of up to 21 days are allowed. Dose delays up to 4 weeks are allowed for participants who require palliative radiotherapy only in consultation with the medical monitor (see [Section 8.1.1](#)).

- The medical monitor must be consulted prior to the restart of study drug after a dose delay.

A participant with a dose delay > 21 days due to an AE, but who has otherwise experienced clinical benefit, in the judgement of the investigator in consultation with medical monitor, may continue to receive study drug.

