#### **4.4.2.1 COVID-19/SARS-CoV-2 Infection or Vaccination**

The following guidelines apply to participants with confirmed (positive by regulatory authority approved/authorized test) or presumed (test pending/clinical suspicion) coronavirus disease 2019 (COVID-19)/severe acute respiratory syndrome coronavirus 2 (SARS-CoV-2) infection:

- For participants with confirmed or presumed SARS-CoV-2 infection, study drug should be delayed for at least 14 days from the start of symptoms. Consideration for study treatment continuation will be made on a case-by-case basis with the medical monitor and the principal investigator.
- Prior to restarting study drug, participants should be afebrile for at least 72 hours and SARS-CoV-2-related symptoms should have recovered to  $\leq$  Grade 1 or baseline for a minimum of 72 hours.
- The sponsor should be informed when resuming study drug.

The sponsor must be informed within 24 hours of awareness of a participant with confirmed or presumed COVID-19/ SARS-CoV-2 infection. Suspected cases of COVID-19/ SARS-CoV-2 should be tested per local practice/institutional guidelines with an approved/authorized test.

At the discretion of the investigator, non-live COVID-19 vaccines may be administered per local practice. Participants may have study drug held to allow for COVID-19 vaccination; delays of up to 5 days are allowed.

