### **5.3 Withdrawal of Participant from the Study**

Participants who withdraw before Study Day 21 (Module A) or Study Day 42 (Module B) during the Dose Escalation Phase for a reason unrelated to drug toxicity may be considered to have inadequate data to support dose escalation. In this case, replacement participants may be enrolled in the same dose level. These participants will be followed for safety assessments (see [Section 12.2](#)).

A participant may be determined to be LTFU after there have been at least 3 documented phone or electronic contact attempts. If this fails, a certified letter should be sent to the participant. Only after these attempts have failed can a participant be determined to be LTFU.

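### Module B: DLT counting stops at Study Day 42 even when the first combined dose is late, so a participant with little or no in-window combination exposure can count as DLT-free

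*Protocol*

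**What the plan says.** **Window.** Protocol 4.2 counts DLTs up to "Study Day 42 of Cycle 1 in the Dose Escalation Phase only for Module B"; Section 4.1.1 gives the period as 42 days. No section says that the cut-off moves.

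**Start of the combination.** Protocol 4.1.1: "In Module B, MGA012 will be administered at a dose of 375 mg (flat dose) Q3W, beginning on Day 22 of Cycle 1". MGC018 is given alone on Day 1.

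**Permitted delays.** Protocol 4.4.2: "For participants in whom the toxicity is assessed to be related to study drug, dose delays of up to 21 days are allowed"; the same limit applies to unrelated toxicity. For COVID-19, Section 4.4.2.1 says "study drug should be delayed for at least 14 days from the start of symptoms".

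**Evaluability.** Section 4.1.1 classes as unevaluable, and replaces, "Participants who require dose delays greater than 21 days secondary to AEs considered unrelated to study treatment" or to any other unrelated cause. Section 5.3 adds that those who withdraw before Day 42 "for a reason unrelated to drug toxicity may be considered to have inadequate data to support dose escalation".

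**Counting.** Protocol 4.3 begins "If 0 of the first 3 participants treated at a given dose level experience a drug-related DLT during the DLT evaluation period". It sets no minimum combination exposure, and the MTD criterion is a DLT incidence below 33%.

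**Analysis sets.** Protocol 14.2 and SAP 4.1 define Safety, Response Evaluable and PSA Response Evaluable populations. Neither defines a DLT-evaluable set.

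**The concern.** The DLTs and MTD of the combination are part of the primary objective, but the combination is given only in the second half of the DLT window. A late Day 22 dose uses up that half, and the end of the window stays where it is.

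Such a delay is foreseeable. Grade 3 neutropenia (Section 7.4.1) and Grade 2 or non-bleeding Grade 3 thrombocytopenia (Section 7.4.2) require a hold, but they are not hematologic DLTs under Section 4.2.1. COVID-19 is a second cause. After these cytopenias MGC018 restarts at a lower level, so the first combined dose may not be at the cohort's own level. The counting rules do not address that case.

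A second route gives no combination exposure at all. A related, non-DLT hold that does not recover within 21 days leads to discontinuation (Sections 7.4.1 and 7.4.2; Section 5.4 unless the sponsor approves). The rule in Section 4.1.1 covers only unrelated delays, and Section 5.3 covers only withdrawals unrelated to toxicity. Neither removes this participant from the count.

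If either kind of participant is counted as DLT-free, the observed DLT rate describes partly MGC018 alone. With 3 to 9 participants per cohort, one of them can change a decision.

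**Working it through.** **1. The plan's own figure.** Days 1–21 are MGC018 alone (21 days). Days 22–42 are the combination (21 days). 21 + 21 = 42, as stated.

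**2. Combination days left after a delay of d days.** Counting the dosing day and Day 42: 42 − (22 + d) + 1 = 21 − d.

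| Delay d (days) | First combined dose | Combination days in window |
|---|---|---|
| 0 | Day 22 | 21 |
| 1 | Day 23 | 20 |
| 7 | Day 29 | 14 |
| 14 | Day 36 | 7 |
| 20 | Day 42 | 1 |
| 21 | Day 43 | 0 |

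With COVID-19 symptoms starting on Day 22, the dose falls on Day 36 at the earliest, which leaves at most 7 days. The exclusion for unrelated delays starts at d = 22, when the count is already zero.

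**3. Effect on escalation: illustration only.** The documents give no DLT risks and no delay frequency. Assumptions:
- combination DLT risk p = 0.40;
- MGC018-alone risk a = 0.10 or 0.20;
- share delayed u = 0.10;
- added risk spread evenly over the 21 combination days;
- delay independent of DLT risk, and no allowance for a reduced MGC018 dose at restart;
- the same-DLT and Grade 4 stopping rules not triggered.

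Counted risk of a delayed participant: r = 1 − (1 − a) × [(1 − p)/(1 − a)]^f, with f = (21 − d)/21.

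Average counted risk: e = (1 − u)p + u·r.

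Probability that the level passes under 3+3+3: with P0 = (1 − e)³ and P1 = 3e(1 − e)², pass = P0 + P1·P0 + P1²·P0.

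All on time, e = 0.40: P0 = 0.216, P1 = 0.432, pass = 0.216 × (1 + 0.432 + 0.1866) = 0.350.

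| d | r (a = 0.20; a = 0.10) | Pass probability |
|---|---|---|
| 0 | – | 35.0% |
| 7 | 0.340; 0.313 | 36.1%; 36.6% |
| 14 | 0.273; 0.214 | 37.4%; 38.6% |
| 21 | 0.200; 0.100 | 38.9%; 40.9% |

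The rise is about 1 to 6 points. With p = 0.25 and u = 0.05 the same formulas give 0.2 to 1.7 points on a base of 67.5%. A larger delayed share gives more. If a = p the shift is zero.

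**4. One affected participant.** Suppose one of the first three has no combination days and, by assumption, no DLT risk on MGC018 alone. The chance of 0 DLTs in 3 then changes from (1 − p)³ to (1 − p)²: from 51.2% to 64.0% at p = 0.20, from 30.1% to 44.9% at p = 0.33, and from 12.5% to 25.0% at p = 0.50.

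**The case against.** **Safeguards.** Protocol 4.3 allows escalation only after the cohort has completed the evaluation period and the medical monitor, an Independent Safety Monitor and the investigators have reviewed the data. "Evaluation of safety data from each cohort will include an assessment of the proportion of participants who receive planned doses"; the review also covers reductions and discontinuations for toxicity, and data beyond the window. Section 4.4.2 requires the medical monitor to be consulted before any restart. Section 4.2.2 makes most Grade 3 or higher non-hematologic events DLTs, and allows some prolonged Grade 2 events to count. That leaves mainly hematologic holds still unresolved at Day 22, and unrelated causes. Table 4 plans no MGC018 level above the monotherapy MTD. All of this stands and limits the consequence. None of it says who is in the denominator.

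**Reading of the counting rule.** Being treated at a dose level, read with Table 4, could be taken to require the combination. The text does not say so, and on that reading these participants have no replacement rule.

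**Stronger readings a reader might infer.**
- *That no rule touches a delayed participant.* By excluding only unrelated delays of more than 21 days, Section 4.1.1 implies that shorter delays stay evaluable. The problem is what that implied rule produces.
- *That any delay leaves 14 days or fewer.* Delays of 1 to 6 days leave 20 to 15.
- *That no DLT display is planned.* SAP 6.8.1 lists none, but SAP Section 7 refers tables and listings to a separate programming plan that is not available here. Only the missing DLT-evaluable definition can be asserted.

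**Conclusion.** The point holds as a counting defect in Module B dose escalation. The day counts rest only on the documents: 20 to 0 in-window combination days for permitted delays of 1 to 21 days, against 21 on schedule. Followed literally, the plan counts such participants, and those who never reach the combination because of a related non-DLT hold, as DLT-free in both the 3+3+3 counts and the below-33% criterion.

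The direction is toward escalation only where the combination carries more DLT risk than MGC018 alone. The size is unknown; the probabilities above rest entirely on assumed risks and delay shares. The documents do not support inferring that the combination MTD will be wrong, because the mandatory review can act on the same information. This should be fixed, with medium confidence. It concerns at most 27 planned participants, before any replacements or enlarged cohorts.

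**What to change.** Reconcile Protocol Sections 4.1.1, 4.2, 4.3, 4.4.2, 5.3 and 5.4. For the Module B escalation counts:

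- **(a) Counting period.** Run it from the first MGC018 dose through the same 21 days from the first combined dose that the on-time schedule already gives (Day 42 if on time). Defining an evaluable set alone would not be enough. After a first combined dose on Day 43, a qualifying event on Day 50 would still fall outside the present cut-off.
- **(b) DLT-evaluable set.** Define it in protocol and SAP as participants who had a DLT in that period, or who received the first combined dose and completed that observation.
- **(c) Replacement and reduced dose.** State that non-evaluable participants are replaced, and how a participant whose first combined dose is at a reduced MGC018 level is counted.
- **(d) Never-combined participants.** Report separately those who never reach the combination because of MGC018-related non-DLT toxicity. Take them to the Section 4.3 review, with the DLT rate shown with and without them, so that replacement does not hide that toxicity.

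No dose, delay limit or treatment rule is proposed. The cost is protocol and SAP wording, one DLT-rate display, and occasionally a few more weeks per cohort or a replacement participant.

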**Table 3 MGC018 Dose Levels: Module A Dose Escalation Phase**

| Cohort    | MGC018 Dose (Q3W) |
|-----------|-------------------|
| Cohort -1 | 0.3 mg/kg         |
| Cohort 1  | 0.5 mg/kg         |
| Cohort 2  | 1.0 mg/kg         |
| Cohort 3  | 2.0 mg/kg         |
| Cohort 4  | 3.0 mg/kg         |
| Cohort 5  | 4.0 mg/kg         |
| Cohort 6  | 5.0 mg/kg         |

For Module A Dose Escalation, if the dose level in Cohort 1 exceeds the MTD, a de-escalation to Cohort -1 dose levels will be employed as summarized in **Table 3**.

**Table 4** **MGC018 and MGA012 Dose Levels: Module B Dose Escalation Phase**

| Cohort    | MGC018 Dose (Q3W) | MGA012 (Q3W) |
|-----------|-------------------|--------------|
| Cohort -1 | MTD-3 (TBD)       | 250 mg (TBD) |
| Cohort 1  | MTD -2            | 375 mg       |
| Cohort 2  | MTD -1            | 375 mg       |
| Cohort 3  | MTD               | 375 mg       |

Note: MTD -2= the dose level that is 2 dose levels below the MTD defined for MGC018 monotherapy.

MTD -1= the dose level that is 1 dose level below the MTD defined for MGC018 monotherapy.

Abbreviations: MTD = maximum tolerated dose; Q3W = every 3 weeks; TBD = to be determined.

For Module B Dose Escalation Phase, if the dose level in Cohort 1 exceeds the MTD, a de-escalation to Cohort -1 dose levels will be employed as indicated in **Table 4**. Depending on the nature and timing of the observed toxicity, the MGC018 dose may be de-escalated to MTD-3, MGA012 may be decreased to 250 mg, or doses of both drugs may be adjusted to other levels at or below the Cohort 1 dose levels, as deemed most appropriate based on review of the cumulative data by the sponsor in consultation with the study investigators.

#### **4.1.2 Cohort Expansion Phase**

During the Cohort Expansion Phase, Module A, participants with relapsed/refractory, unresectable locally advanced or metastatic mCRPC, NSCLC, TNBC, SCCHN, and melanoma will receive MGC018 alone at the recommended phase II dose (RP2D) based on safety, PK, and antitumor activity from the Dose Escalation Phase of the study. The RP2D for the Cohort Expansion Phase of Module A was determined based on the review of the safety, tolerability, and PK data. Participants in Module A Cohort Expansion Phase will receive 3 mg/kg every 3 weeks. The MGC018 dose will be capped for participants with a body weight  $\geq 100$  kg.

During the Cohort Expansion Phase, Module B, cohorts of participants with unresectable, locally advanced or metastatic SCCHN or mCRPC, and a cohort of participants with tumor type TBD, based on the prior experience with Module A and Module B (including any evidence of emerging antitumor activity in a given tumor type) will be treated with MGC018 in combination with MGA012 at the MTD/MAD dose based on the safety, PK and antitumor activity from the Dose Escalation Phase of the study for Module B. See **Table 5** for an overview of the Expansion Cohort.

**Table 5** Expansion Cohorts

| Expansion Cohort per Module | Tumor Type     | Planned Enrollment |
|-----------------------------|----------------|--------------------|
| Module A                    | mCRPC          | Up to 16           |
| Module A                    | NSCLC          | Up to 16           |
| Module A                    | TNBC           | Up to 16           |
| Module A                    | SCCHN          | Up to 16           |
| Module A                    | Melanoma       | Up to 16           |
| Module B                    | SCCHN          | Up to 16           |
| Module B                    | mCRPC          | Up to 16           |
| Module B                    | Tumor Type TBD | Up to 16           |

Abbreviations: mCRPC = metastatic castrate-resistant prostate carcinoma; NSCLC = non-small cell lung cancer; SCCHN = squamous cell cancer of the head and neck; TBD = to be determined; TNBC = triple negative breast cancer.

## 4.2 Dose Limiting Toxicity

For the purposes of guiding study decisions regarding dose escalation, DLTs will be based on study drug-related AEs or laboratory abnormalities that occur up to Study Day 21 of Cycle 1 in the Dose Escalation Phase only for Module A and Study Day 42 of Cycle 1 in the Dose Escalation Phase only for Module B. The severity of AEs will be graded according to the National Cancer Institute Common Terminology Criteria for Adverse Events version 4.03 (NCI CTCAE v4.03). Dose-limiting toxicities will be defined separately for hematologic, non-hematologic, and hepatic non-hematologic events.

In general, for participants who experience toxicity that may meet the criteria for a DLT, subsequent administration of the study drugs should be held pending management and/or resolution of the event and assessment of attribution to the study drug. Criteria for discontinuation of therapy are outlined in [Section 5.4](#).

